Pen Bay Medical Center
MaineHealth

Official Title: ATIVO Study – Anticoagulation Therapy In The Very Old

NCT #: 03103763

Protocol Version 2.1, dated 13 DEC 2018

**ATIVO STUDY
ANTICOAGULATION THERAPY IN THE VERY OLD**

Principal Investigators: *[name]*
[name]
Penobscot Bay Medical Center
Anticoagulation Service

List of Abbreviations

ACS – Penobscot Bay Medical Center Anticoagulation Services

PBMC – Penobscot Bay Medical Center

TTR – Time in Therapeutic Range

1 Introduction:

Atrial fibrillation increases the risk of stroke by allowing the formation of clot within the left atrium and left atrial appendage. This clot is then able to embolise to the cerebral circulation producing vascular occlusion and stroke often with severe disabling deficit or death. Anticoagulation has been shown to substantially decrease the risk of stroke in patients with atrial fibrillation. Unfortunately anticoagulation increases the risk of major hemorrhage. Almost 15% of patients with atrial fibrillation followed by the Pen Bay Anticoagulation Service are over 90 years old. There is presently no clear guidance for anticoagulation in the very old. Our preliminary data suggest that in this very old group there is an increased risk of both thrombotic and hemorrhagic complications but that stroke prevention can be safely achieved.

2 Study Objectives

This study is designed to evaluate the efficacy and safety of warfarin anticoagulation in the very old and attempt to identify risk factors which may impede safe and effective anticoagulation.

3 Study Design

This is a prospective registry study with data being collected continuously for 24 months.

4 Subject Selection and Withdrawal

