Official Title: **ATIVO Study – Anticoagulation Therapy in the Very Old**

NCT #: **03103763**

Statistical analysis plan

For the purpose of this study, we attempted to detect differences in outcomes among age groups (70-79, 80-89, and 90+) undergoing anticoagulation therapy at study enrollment and in 6-month intervals for 24 months. Descriptive statistics were used to summarize the demographic (age group, sex, and living arrangement) and clinical characteristics (mobility, alcohol use, CHADS2-VASc, Fragility score, mini Cog, and mobility scale) of patients included in the study, with continuous variables presented as a mean +- standard deviation and categorical variables as frequencies/percentages of the total. The primary outcome of interest was time in therapeutic range (TTR), a percentage of time that a patient's International Normalized Ratio (INR) values were in range over a 6-month period. Secondary outcomes were all-cause mortality, stroke, and major bleeding events. Student t tests and chi-squared tests were conducted to compare data between groups. Statistical significance was set at $P < .05$ with a 95% confidence interval.

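### The stated aim is to evaluate safety in the very old, but the SAP plans only between-decade difference tests and no estimate of the 90+ event risks or of their excess over younger decades

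*Protocol*

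**What the plan says.** - **Objective.** Protocol Section 2: "This study is designed to evaluate the efficacy and safety of warfarin anticoagulation in the very old". A second aim is to look for risk factors that stand in the way of safe and effective treatment.
- **Background.** Protocol Section 1: "Our preliminary data suggest that in this very old group there is an increased risk of both thrombotic and hemorrhagic complications". The same sentence goes on to say that "stroke prevention can be safely achieved".
- **Aim of the analysis.** SAP: "we attempted to detect differences in outcomes among age groups", the groups being 70-79, 80-89 and 90+.
- **Methods.** SAP: "Student t tests and chi-squared tests were conducted to compare data between groups". The threshold follows: "Statistical significance was set at" P < .05, with a 95% confidence interval named in the same sentence but not attached to any rate, mean or difference.
- **Descriptive statistics.** The SAP specifies these for demographic and clinical characteristics. It does not specify them for outcome events.
- **Outcomes.** TTR is primary. All-cause mortality, stroke and major bleeding are secondary.
- **Protocol Section 6.** A list of characteristics and events to be compared across decades, with no method, reference level or margin.
- **Group sizes.** Protocol Section 4.3 approaches every eligible patient aged 90 or over and enrols equal numbers from each younger decade. No sample size is given.

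**The concern.** Whether anticoagulation is acceptably safe at 90+ depends on two quantities: the level of event risk in that group, and the largest excess over younger patients that the data leave open. The SAP commits to reporting neither with a measure of uncertainty. A test of no difference answers another question, namely whether the data are incompatible with equal risk. That remains so when the test is exact and correctly sized, so this is not a complaint about chi-squared in sparse tables.

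At stake is how the result will be read. The Introduction says that clear guidance for this age group is lacking, so clinicians may rely on what the registry reports. If the groups turn out small, a substantial excess of bleeding or stroke at 90+ could coexist with P >= .05, and without intervals readers could not see how much had been left open.

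**Working it through.** The documents give no sample size, event rate, power or margin, so there is no figure of the plan's own to reproduce. What follows is illustration. Assumed: 50 to 200 subjects per decade, and 24-month risks of 5% or 8% in a younger decade, doubling at 90+. From the documents: equal group sizes (Protocol Section 4.3), 24 months of follow-up (Section 3), chi-squared test and P < .05 (SAP). The test is taken as two-sided, for one pair of decades, without continuity correction.

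**1. How often a true doubling is non-significant.** With x1 and x2 events among n subjects in each group, p1 = x1/n, p2 = x2/n and pooled p = (x1 + x2)/(2n):

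X² = (p1 − p2)² / [p(1 − p)(2/n)]

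The result is non-significant when X² < 3.84. Binomial probabilities were summed over all such pairs (x1, x2).

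| n per decade | 8% vs 16%: share with P >= .05 | 5% vs 10%: share with P >= .05 |
|---|---|---|
| 50 | 76% | 86% |
| 75 | 67% | 78% |
| 100 | 58% | 73% |
| 150 | 42% | 63% |
| 200 | 30% | 53% |

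For 5% vs 10%, 80% power needs 435 per group.

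**2. What an interval would show if the groups looked identical.** Suppose 8% is observed in both. The Newcombe interval has half-width √[(0.08 − L)² + (U − 0.08)²], where L and U are the Wilson limits for one group.
- n = 50: L = 3.15%, U = 18.84%. Half-width √(4.85² + 10.84²) = 11.9 points.
- n = 100: L = 4.11%, U = 15.00%. Half-width √(3.89² + 7.00²) = 8.0 points.
- n = 200: L = 4.98%, U = 12.60%. Half-width √(3.02² + 4.60²) = 5.5 points.

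A doubling is an excess of 8 points. It is not excluded at 50, lies at the limit at 100, and is excluded at 200. The test gives the same P value, 1, in all three cases. Only the interval separates them.

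**3. What the 90+ group alone would show.** Exact (Clopper-Pearson) 95% intervals:
- 5 events in 50: 3.3% to 21.8%.
- 10 events in 100: 4.9% to 17.6%.
- No events: the upper limit is 1 − 0.025^(1/n), which is 7.1%, 3.6% and 1.8% at n = 50, 100 and 200.

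These describe the risk at 90+ directly. No between-group test supplies them.

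**4. What no comparison of decades can show.** Every subject is recruited from, and followed by, the anticoagulation service (Protocol Sections 4.1 to 4.3). No group without anticoagulation is described. Similar risks across decades would therefore show similarity among treated patients, not that treatment is safe or effective in any of them.

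**The case against.** A reader might infer that the investigators mean to offer a non-significant P value as proof of safety. The documents do not support that. Neither the SAP nor Protocol Section 6 contains such a rule. The statement that prevention can be achieved safely is background on preliminary data, and its own sentence reports more thrombotic and hemorrhagic complications in the very old. The investigators' view of safety therefore does not rest on finding no difference between ages; a significant excess at 90+ would agree with their preliminary data.

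It can also be said that Section 2 is a neutral aim of a registry, that TTR is primary, and that no confirmatory safety claim is made. All of this is correct. It lowers the weight of the point but does not supply the missing estimates.

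The SAP does mention a 95% confidence interval, and a comparison by decade would ordinarily show counts. But the interval belongs to no stated quantity, and the planned descriptive statistics stop at baseline and clinical characteristics.

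Finally, the size depends on unstated inputs. It would be too strong to say that a doubling would usually be missed: for 8% vs 16% that fails at 150 and 200 per decade (42% and 30% non-significant). This stands, and it is why the range is shown.

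**Conclusion.** The concern holds as a mismatch between objective and analysis. The safety objective has no matching estimate: the plan tests whether decades differ but does not commit to reporting the event risk at 90+ or the excess that remains possible. It does not hold as a charge that the plan equates non-significance with safety; that is a possible misreading which the plan does nothing to prevent.

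The chance that a true doubling goes undetected runs from 30% to 76% (8% vs 16%) or from 53% to 86% (5% vs 10%) across 200 down to 50 subjects per decade. These figures rest wholly on assumed sizes and risks. The mismatch itself does not, since it would remain at any sample size.

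The change should be made. Its importance is moderate, because this is an observational registry and these outcomes are secondary. A non-inferiority margin between decades is not the remedy, because every decade is drawn from the anticoagulation service.

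**What to change.** In the SAP, make estimation the main analysis of stroke, major bleeding and all-cause death:

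1. Report the 24-month risk of each outcome in each decade, with numerator, denominator and exact 95% confidence interval.
2. Report the differences 90+ minus 80-89 and 90+ minus 70-79, each with a 95% confidence interval.
3. Base any statement about safety on the absolute risks at 90+ and on these limits, and state that P >= .05 will not be interpreted as equal safety.
4. State that, because all subjects come from the anticoagulation service, comparisons between decades do not show the effect of anticoagulation itself.

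The chi-squared tests may stay as a supplement. No new data are needed. The cost is a few sentences and some table columns; the downside is that the conclusion on safety will probably have to be worded more cautiously.

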5.2 Follow Up

Every 6 months (+/- 4 weeks), subjects will be contacted and follow up information will be obtained. When possible, these visits will be conducted when the subject has an appointment at the ACS and will be done in person. If the subject is no longer being seen by the ACS, information will be obtained by phone or by searching the subject's medical record. If needed, family or friends as designated by the subject at study enrollment, will be contacted in order to obtain information about the subject outcomes.

If the subject was enrolled utilizing an LAR, the study will be re-explained and assent will be obtained and documented in the source document prior to any study procedures.

Follow up Mini-Cog™ evaluations will only be done if the visit is done in person. See attached Follow-Up Data Collection Form for details regarding what information will be obtained at these visits.

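### The protocol aims to identify risk factors for unsafe or ineffective anticoagulation, but neither document specifies a patient-level analysis of any factor other than age

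*Protocol*

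**What the plan says.** Protocol section 2 has two aims. The first is to evaluate the efficacy and safety of warfarin in the very old. The second is to "attempt to identify risk factors which may impede safe and effective anticoagulation".

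Protocol section 6 is the only analysis text in the protocol. It gives one instruction, comparison by decade, over a single list that mixes candidate factors (sex, living arrangement, alcohol use, CHA2DS2-VASc, HAS-BLED, frailty, mobility) with outcomes (TTR, deaths, hospitalizations, major bleeding, stroke types).

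The SAP is one paragraph. Its purpose reads "we attempted to detect differences in outcomes among age groups (70-79, 80-89, and 90" and over, assessed "at study enrollment and in 6-month intervals for 24 months". On the other factors it says "Descriptive statistics were used to summarize the demographic (age group, sex, and living arrangement) and clinical characteristics", the latter being "mobility, alcohol use, CHADS2-VASc, Fragility score, mini Cog, and mobility scale". The primary outcome is TTR over a 6-month period. On the rest, "Secondary outcomes were all-cause mortality, stroke, and major bleeding events". The only inferential statement is "Student t tests and chi-squared tests were conducted to compare data between groups".

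**The concern.** An aim to identify risk factors needs an analysis in which a patient's factor is set against that same patient's outcome. Neither document describes one, except for age group. HAS-BLED shows the gap most clearly: Protocol section 5.4 presents it as a tool for stratifying bleeding risk, yet section 6 only compares it by decade and the SAP does not name it.

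If the plan is run as written, the second aim is answered for age group alone. Whether or not TTR or bleeding differs by decade, the study could not say whether frailer, cognitively impaired or less mobile patients within a decade do worse, although frailty, Mini-Cog and mobility are all collected.

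**Working it through.** **1. Each factor against each analysis statement.**

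| Factor | Protocol section 6 | SAP | Patient-level analysis against an outcome |
|---|---|---|---|
| Sex | by decade | described | none specified |
| Living arrangement | by decade | described | none specified |
| Alcohol use | by decade | described | none specified |
| CHA2DS2-VASc | by decade | described | none specified |
| HAS-BLED | by decade | not named | none specified |
| Frailty scale | by decade | described | none specified |
| Mobility | by decade | described | none specified |
| Mini-Cog | not listed | described | none specified |

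Eight factors and four SAP outcomes make 8 × 4 = 32 possible pairs. The documents specify an analysis for 0 of them.

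**2. Could the decade tables answer the aim indirectly?** All counts here are assumed, for illustration: 100 patients per decade, 20%, 40% and 60% frail, and 5%, 10% and 15% with a major bleed. In scenario A frailty is unrelated to bleeding within each decade. In scenario B every bleed is in a frail patient.

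| Decade | Frail | Bleeds | A: frail / non-frail bleeds | B: frail / non-frail bleeds |
|---|---|---|---|---|
| 70-79 | 20 | 5 | 1 / 4 | 5 / 0 |
| 80-89 | 40 | 10 | 4 / 6 | 10 / 0 |
| 90+ | 60 | 15 | 9 / 6 | 15 / 0 |
| Total | 120 | 30 | 14 / 16 | 30 / 0 |

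- Scenario A, within decade: 1/20 against 4/80 (5% each), 4/40 against 6/60 (10% each), 9/60 against 6/40 (15% each). The risk ratio is 1.0 in every decade.
- Scenario A, decades pooled: 14/120 = 11.7% against 16/180 = 8.9%, a ratio of 1.31 produced by age alone.
- Scenario B: 30/120 = 25% against 0/180.

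The columns that section 6 would tabulate (frail by decade, bleeds by decade) are the same in A and B. The planned tables therefore cannot separate a strong risk factor from none. The pooled ratio of 1.31 in A also shows that a crude test of frailty against bleeding would not be enough, because age group has to be in the analysis.

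**3. Which TTR values can serve.** The SAP's time points give TTR at enrollment and at 6, 12, 18 and 24 months. Protocol section 5.4 computes TTR over the preceding 6 months, so the enrollment value covers time before the enrollment factors were recorded. Four follow-up values remain.

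**4. Multiplicity.** Six factors for TTR, each tested at 0.05 and taken as independent, give 1 − 0.95^6 = 1 − 0.735, or about a 26% chance of at least one false positive.

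**5. What cannot be computed.** The documents state no sample size, TTR standard deviation or event rate. Section 4.3 fixes only that the younger decades match the oldest in number. No confidence-interval width or power can be derived from the documents.

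**The case against.** - **The SAP's test sentence does not say which groups it means.** This stands as a limit on wording. Groups defined by frailty or another factor are not strictly excluded, so the accurate statement is that no such analysis is specified. None is named, however, and the SAP's stated purpose is age groups. If factor-defined groups were meant, the SAP should say so, and unadjusted tests would still mix the factor with age.
- **The aim is hedged and secondary.** The protocol only undertakes to attempt it, and the SAP makes no risk-factor claim. This stands as a reason to ask for exploratory work only. An exploratory aim still needs a factor-outcome analysis, or a conclusion limited to what was analysed.
- **The study is an unfunded registry at one service, events may be few, and the SAP is written in the past tense.** This stands too. It argues for simple estimates, a post hoc label where it applies, and no bleeding model without enough events.
- **A reader might infer that the age comparisons are compromised, or that one large multivariable model is required.** The documents support neither. A crude comparison by decade answers the question of how outcomes differ by age. A joint model of frailty, mobility, Mini-Cog and living arrangement would condition each factor on overlapping measures, which is not the within-decade question.

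**Conclusion.** The concern holds in this form: a stated aim has no specified analysis except for age group. Its size is 0 of 8 non-age factors related at patient level to any of 4 outcomes. That count rests on the text alone. The frailty illustration rests on assumed counts and serves only to show that decade tables cannot substitute.

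No planned age result is invalid. It cannot be claimed that factor-outcome tests were never run, only that none is specified. Nor can it be claimed that the added estimates would be precise enough to be decisive. The data collection forms are not available, so other factors may be recorded, but forms would not supply an analysis. The change is worth making because it lets the study address its own second aim, or stops the report from appearing to.

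**What to change.** Keep every decade comparison and add to the SAP a short exploratory section, labelled post hoc if data have already been analysed.

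- **TTR.** Fit a repeated-measures model of the 6-, 12-, 18- and 24-month values on age group plus one enrollment factor at a time: frailty, Mini-Cog, mobility, living arrangement, alcohol use, sex. Leave out the enrollment TTR.
- **Missing TTR.** Tabulate the TTR intervals contributed by each level of each factor. Values may be missing after death or after a patient leaves the service. Protocol section 5.2 foresees departures ("If the subject is no longer being seen by the ACS, information will be obtained by phone") without saying whether INR values remain available.
- **Major bleeding.** If event counts allow, fit age group plus frailty and, separately, age group plus HAS-BLED. Otherwise describe bleeding.
- **Stroke and death.** Describe.
- **Reporting.** Give all factor estimates with 95% confidence intervals rather than significance statements, since several factors are examined.
- **If these analyses are not run.** Limit the risk-factor conclusion to age group and state that the other factors were only described.

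The cost is SAP wording and modest extra analysis of factors already collected. The coding of living arrangement and alcohol use must be checked against the collection forms. Confidence intervals may be wide, especially for bleeding. The fallback costs one sentence.

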4.1 Inclusion Criteria

1. Subject must be 70 years of age or older
2. Subject must have electrocardiographically confirmed atrial fibrillation
3. Anticipated regular follow with patient by PBMC Anticoagulation Services
4. Subject (or legally authorized representative) must be willing to provide informed consent

4.2 Exclusion Criteria

1. Patients not being followed by the PBMC Anticoagulation Services will be excluded from the study.

4.3 Subject Recruitment and Screening

Subjects will be recruited from the PBMC Anticoagulation Services (ACS) department. The medical records used by the ACS will be searched using age ≥ 70 and diagnosis of atrial fibrillation as search criteria. All patients aged 90 years or older who fit the criteria will be approached about participation in the study.

An equal number of patients from the ACS who are aged 80-89 years and, an equal number of patients from the ACS will be enrolled who are aged 70-79 years will be enrolled.

4.4 Early Withdrawal of Subjects

Subjects may withdraw from study participation at any time without any effect on their care at the ACS. Additionally, subjects will be withdrawn early from the study if the investigators are unable to communicate with them or obtain medical records.

5 Study Procedures

5.1 Enrollment

At the enrollment visit, after obtaining written informed consent, information will be obtained from the subject and/or caregiver, as well as from the medical record.

All evaluations will be performed by a trained clinician. See attached Baseline Data Collection Form for all the information that will be obtained at this visit.

5.2 Follow Up

Every 6 months (+/- 4 weeks), subjects will be contacted and follow up information will be obtained. When possible, these visits will be conducted when the subject has an appointment at the ACS and will be done in person. If the subject is no longer being seen by the ACS, information will be obtained by phone or by searching the subject's medical record. If needed, family or friends as designated by the subject at study enrollment, will be contacted in order to obtain information about the subject outcomes.

If the subject was enrolled utilizing an LAR, the study will be re-explained and assent will be obtained and documented in the source document prior to any study procedures.

Follow up Mini-Cog™ evaluations will only be done if the visit is done in person. See attached Follow-Up Data Collection Form for details regarding what information will be obtained at these visits.

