5.4 Assessments

Mini-Cog™ (used by permission) is a validated screening tool used to detect dementia.⁵

CHA₂DS₂-VASc score is a validated tool for stroke risk stratification.³

HAS-BLED score is a validated schema for risk stratification for bleeding events among anticoagulated patients.¹

Dalhousie University Clinical Frailty Scale is a simplified scale to assess frailty.⁴

Mobility score is a simple noting of patient mobility at each visit- ambulating without assist, ambulating with cane, ambulating with walker, or arrived in wheelchair.

Time in Therapeutic Range (TTR) will be calculated utilizing the Rosendaal method of percentage days in therapeutic range in the past 6 months.

6 Analysis Plan

Compare by decade:

Sex

Living arrangement

Alcohol use

CHA2DS2-VASc score

HAS-BLED score

Dalhousie University Clinical Frailty Scale

Mobility score

TTR for 2 years and best and worse 6 months

Death secondary to anticoagulation

Death secondary to cardiovascular causes

Number of hospitalizations

Major bleeding defined as any bleeding meeting at least one of the following criteria:

- Fatal bleeding
- Symptomatic bleeding in a critical area or organ, such as intracranial, intraspinal, intraocular, retroperitoneal, intraarticular or pericardial or intramuscular with compartment syndrome, and/or
- Bleeding causing a fall in hemoglobin level of 2 g/dl or more, or leading to transfusion of two or more units of whole blood or red cells.²

CNS Bleeds with death, disability, or no disability

Embolic ischemic stroke

Non embolic ischemic stroke

Mechanism unknown ischemic stroke

Hemorrhagic stroke non traumatic

Traumatic intracerebral hemorrhage

Traumatic subdural hemorrhage

Cardiovascular events (non stroke type)

7 Confidentiality

Subject information will be kept in the PBMC Clinical Research office which is locked when unattended. Information entered into a database will be housed on a PBMC shared drive which is password protected. Information about study subjects will be kept confidential and managed according to the requirements of the Health Insurance Portability and Accountability Act of 1996 (HIPAA).

- Protected health information (PHI) which will be collected from subjects in this study include, demographics, medical history, medication list, information related to adverse events, symptoms related to atrial fibrillation and the use of anticoagulants.
- The investigator and his designees will have access to this information.

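### Outcomes are collected after subjects leave the anticoagulation service, but no rule separates events and time on and off warfarin, so the age comparison of strokes, bleeds and deaths may mix the two

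*Protocol*

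**What the plan says.** The objective in protocol section 2 is specific to one drug: "This study is designed to evaluate the efficacy and safety of warfarin anticoagulation in the very old". It also seeks factors that stand in the way of safe and effective anticoagulation.

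Entry depends on expected contact with the service ("Anticipated regular follow with patient by PBMC Anticoagulation Services", section 4.1). No criterion requires warfarin by name.

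Section 5.2 expects some subjects to leave the service and keeps them in follow-up: "If the subject is no longer being seen by the ACS, information will be obtained by phone or by searching the subject's medical record". Where necessary, relatives or friends "will be contacted in order to obtain information about the subject outcomes". Apart from a subject's own choice, section 4.4 gives one ground for early withdrawal: "subjects will be withdrawn early from the study if the investigators are unable to communicate with them or obtain medical records". Stopping warfarin and leaving the ACS are not on that list.

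For the analysis, protocol section 6 opens with "Compare by decade" and lists deaths by cause, hospitalizations, major bleeding and several stroke types. The SAP says "we attempted to detect differences in outcomes among age groups (70-79, 80-89, and 90+) undergoing anticoagulation therapy at study enrollment"; the same sentence goes on to add six-month intervals over 24 months. It makes TTR primary and all-cause mortality, stroke and major bleeding secondary, and it names t tests and chi-squared tests. Neither document has an on-treatment period, a censoring rule, a rule for switching, or discontinuation of warfarin as an outcome.

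**The concern.** The question is about warfarin, but the events to be compared are not tied to warfarin use. As written, a stroke long after a subject stopped the drug is handled like a stroke on the drug, and bleed-free months off the drug add to its apparent safety. If the oldest subjects spend more of their follow-up off warfarin, their bleeding can look lower and their stroke risk higher than the on-warfarin rates would show, even with no true difference by age.

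TTR can be calculated only where there are INR values on warfarin, while strokes, bleeds and deaths are collected throughout. The primary and secondary results may therefore describe different periods and partly different patients. Stopping warfarin also bears directly on the section 2 aim of finding what impedes safe and effective anticoagulation, yet it is not among the items compared by decade.

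**Working it through.** The documents state no sample size, event rate or discontinuation rate, so there is no figure of the plan's own to reproduce. The check has two parts.

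**1. The text.** Section 5.2 keeps outcome collection going after a subject leaves the ACS, and section 4.4 does not withdraw such a subject. Section 6 and the SAP group events by age only. Section 4.2 states "Patients not being followed by the PBMC Anticoagulation Services will be excluded from the study", but it stands among the selection criteria. Read as a continuing exclusion, it would contradict section 5.2, so it does not supply the missing rule. The gap in the analysis plan is confirmed.

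**2. The possible size.** Let f be the share of a decade's follow-up time spent off warfarin. Then

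observed rate = (1 − f) × on-warfarin rate + f × off-warfarin rate.

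All inputs here are assumptions, per 100 person-years, and are the same in both decades:
- Bleeding: 5 on warfarin, 1 to 3 off.
- Stroke: 2 on warfarin, 4 to 6 off.

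Worked example, bleeding with an off-rate of 1 and shares of 10% versus 40%:
- 70-79: 0.90 × 5 + 0.10 × 1 = 4.6
- 90+: 0.60 × 5 + 0.40 × 1 = 3.4
- ratio: 3.4 / 4.6 = 0.739

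Worked example, stroke with an off-rate of 6 and the same shares:
- 70-79: 0.90 × 2 + 0.10 × 6 = 2.4
- 90+: 0.60 × 2 + 0.40 × 6 = 3.6
- ratio: 3.6 / 2.4 = 1.500

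| Off-time, 70-79 vs 90+ | Apparent bleeding ratio (off-rate 1 to 3) | Apparent stroke ratio (off-rate 4 to 6) |
|---|---|---|
| 20% vs 20% | 1.000 | 1.000 |
| 5% vs 10% | 0.958 to 0.980 | 1.048 to 1.091 |
| 5% vs 20% | 0.875 to 0.939 | 1.143 to 1.273 |
| 10% vs 30% | 0.826 to 0.917 | 1.182 to 1.333 |
| 10% vs 40% | 0.739 to 0.875 | 1.273 to 1.500 |

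The on-warfarin ratio is 1.00 in every row.

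A true difference can also be diluted. Assume bleeding of 3 versus 6 on warfarin and 1 versus 2 off, a true ratio of 2.0:
- 5% vs 10%: (0.90 × 6 + 0.10 × 2) / (0.95 × 3 + 0.05 × 1) = 5.6 / 2.9 = 1.93
- 10% vs 40%: (0.60 × 6 + 0.40 × 2) / (0.90 × 3 + 0.10 × 1) = 4.4 / 2.8 = 1.57

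The SAP's chi-squared test compares proportions, not rates. At these rates that matters little. Over two years, (1 − e^−0.068) / (1 − e^−0.092) = 0.0657 / 0.0879 = 0.75, against a rate ratio of 0.74.

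**The case against.** Several stronger readings are tempting, and the documents do not support them.

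- **That later events are counted under the enrollment decade.** Recruitment by decade makes this the natural reading, but no text says whether age group is fixed at enrollment. The SAP sentence, read to its end, could describe assessment times or groups on anticoagulation at each interval.
- **That leaving the ACS means stopping warfarin.** A subject may have moved, or may continue warfarin under other care. The group may include subjects who stopped or switched; the text does not say that it does.
- **That exposure is not recorded.** Protocol section 7 lists medications and anticoagulant use among the information collected, and the follow-up form attached to the protocol was not available for this review. Only the analysis rule can be shown to be absent.
- **That no event is tied to exposure.** Section 6 has an item for deaths attributed to anticoagulation. All-cause mortality, strokes and bleeds remain unseparated.
- **That the study could declare 90+ safer but less well protected through discontinuation alone.** Assume 500 subjects per decade with two full years each (1,000 person-years). The most extreme row gives 24 versus 36 strokes, z = 12/√60 = 1.55, and 46 versus 34 bleeds, z = 12/√80 = 1.34. Neither reaches 1.96. Estimates would shift, but a significant false finding would not be expected at that size.

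Two further points stand. First, outcomes in everyone anticoagulated at enrollment are a legitimate registry question, and following subjects after they leave the ACS is good practice. Second, an on-warfarin analysis has its own bias, because stopping is not random. Subjects who switch to another anticoagulant also need not show the lower bleeding and higher stroke rates assumed above. These points argue for saying which question each analysis answers and showing both; they do not supply the missing rule.

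**Conclusion.** The concern holds in a limited form. The plan collects outcomes beyond ACS care, states a question about warfarin, and has no rule separating events and time on and off the drug. The comparisons at risk are the secondary ones: stroke, major bleeding and death. Events off warfarin do not distort TTR.

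A between-decade distortion of the kind illustrated requires time off warfarin to differ by age, and the documents do not say whether it does. Under the assumed rates it ranges from negligible (a few percent either way for bleeding, 5% to 9% for stroke) to material (bleeding about 12% to 26% too low, stroke 27% to 50% too high), and it is nil if off-time is equal. These figures are illustrations from assumed inputs, not estimates for this study. The change is worth making because it is cheap and bears directly on the study's own objective.

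**What to change.** 1. Keep the section 5.2 follow-up as it is, and reconcile it with section 4.2 by saying that 4.2 applies at entry, if that is the intent.
2. Confirm that the follow-up form captures current warfarin status, the date of any stop or switch, and the reason. Add these if it does not. If collection has closed, look for them in the medication lists and ACS records.
3. State that age group is fixed at enrollment.
4. In section 6 and the SAP, report stroke, major bleeding and death by decade as rates per on-warfarin person-time, with a lag after stopping that is fixed before the results are seen. Give rate ratios with 95% confidence intervals, since a chi-squared test on counts takes no account of person-time. Show the all-follow-up results beside them. Say that the first describes subjects while on warfarin and the second describes everyone enrolled, whatever happened later.
5. Add permanent discontinuation of warfarin, with reason, to the items compared by decade.

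The cost is at most two or three form fields and one SAP paragraph. If the events have already been compared by age group, label the on-warfarin analysis as added afterwards. The drawback is that it rests on fewer events and stopping is informative, so it should accompany the all-follow-up comparison and not replace it.
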